7.1 Demographic and Baseline Characteristics

For the subjects in FAS, demographic information and baseline values will be summarized by descriptive statistics. Categorical data will be summarized by number and

percent; and quantitative data will be presented by the number of subjects, mean, standard deviation, minimum value, median, and maximum value.

The following demographic and baseline values will be summarized.

Continuous variables:

- Age (years)
- Body Weight (kg)
- Body Height (cm)
- Body mass Index (kg/m²)
- Blood Pressure (systolic/diastolic) (mmHg)
- Pulse (bpm)
- Respiratory Rate (rpm)
- Body Temperature (°C)
- Duration of Generalized Pustular Psoriasis (GPP) [years: [Date of first dose of study drug – Date of first diagnosis of GPP]/365.25]
- Body Surface Area (BSA; percent [%])
- Psoriasis Area and Severity Index (PASI) score [0.0-72.0]
- Dermatology Life Quality Index (DLQI) [0-30]
- Short Form 36 Health Survey (SF-36)

Categorical variables:

- Sex [male/female]
- Race
- Ethnicity
- Age categories [< 65, \geq 65]
- Age categories [< 30, 30 - < 50, \geq 50]
- Body Weight categories [Median]

- Medical History (using MedDRA, Version 19.1)
- Tobacco [Current, Former, Never, Unknown]
- Alcohol use [Current, Former, Never, Unknown]
- PASI [< 10 , $10 - < 30$, ≥ 30]
- BSA [$< 10\%$, $10 - < 25\%$, $25 - < 50\%$, $50 - < 75\%$, $75 - < 100\%$]
- Tuberculin PPD skin test result
- Chest x-ray finding [finding, calcified granulomas, pleural scarring, pleural thickening, sign of active TB, previous TB infection]
- Antinuclear antibody (ANA) [positive/negative]
- Anti-double stranded DNA (dsDNA) [positive/negative]
- Physician's Global Assessment (PGA) [clear (score=0), minimal (score=1), mild (score=2), moderate (score=3), severe (score=4), very severe (score=5)]

7.2 Medical History

For the FAS population, the medical history data will be summarized and presented using body systems and conditions/diagnoses as captured on the eCRF. The body systems will be presented in alphabetical order and the conditions/diagnoses will be presented in alphabetical order within each body system. The number and percentage of subjects with a particular condition/diagnosis will be summarized. Subjects reporting more than one condition/diagnosis within a body system will be counted only once for that body system.

In addition, the medical history data for each subject will be provided in the listing.

Chest X-Ray Results

All subjects undergo a standard chest x-ray of chest (including a posterior-anterior [PA] and lateral views) at the screening visit. Finding status (Normal, Abnormal), findings on calcified granulomas (Absent, Present), pleural scarring/thickening (Absent, Present), signs of active TB (Yes, No), and findings indicative of previous TB infection (Yes, No) will be summarized by number and percentage of subjects with these findings.

TB Test Results

Results of Tuberculin PPD skin test or Interferon-Gamma Release Assay (IGRA; QuantiFERON-TB Gold In-Tube test or T-SPOT TB test) at screening visit will be summarized by results.

- Tuberculin PPD skin test (Negative [Induration < 5 mm], Positive [Induration \geq 5 mm])
- IGRA (Negative, Positive, Indeterminate)

ECG Results

ECG results at screening will be presented as frequency distribution showing results as Normal, Abnormal (Not clinically significant), Abnormal (Clinically significant) and Unable to evaluate/missing.

Pregnancy Tests

Pregnancy information collected at screening (serum test), baseline and Week 52/premature discontinuation (urine test) visits will be listed.

Pharmacokinetic

Adalimumab trough serum concentrations will be reported at each time point using descriptive statistics. The relationship between adalimumab concentrations and Clinical Response will be determined as appropriate.

Immunogenicity

AAA will be evaluated for each subject and rates of AAA positive will be calculated. As appropriate, the effect of AAA on adalimumab pharmacokinetics, efficacy variable(s), and treatment-emergent adverse events may be evaluated.

7.3 Prior and Concomitant Therapy

Prior and concomitant therapy using drug generic name coded using WHO Drug dictionary (version 2016Q1) will be summarized by the generic name with counts and percentages.

8.0 Patient Disposition

Subject disposition will be presented for subjects in the safety analysis set using the following information

- Number and percent of subjects in various analysis sets by investigator and site number
- For the interim analysis at Week 24, number and percent of subjects completing Week 24 and discontinuing on or before Week 24 visit
- For the interim analysis at Week 24, subject disposition including the number and percent of subjects who prematurely discontinued the study (on or before Week 24) by primary reason and by any reason
- For the final analysis at Week 52, number and percent of subjects completing Week 52 and discontinuing before Week 52 visit
- For the final analysis at Week 52, subject disposition including the number and percent of subjects who prematurely discontinued the study (before Week 52) by primary reason and by any reason
- Number and percent of subjects by visit

Summary of protocol deviations will be provided.

The number and percentage of screened subjects who screen failed and the reasons for screen failure (inclusion/exclusion criteria, withdrew consent, lost to follow-up, and/or other) will be summarized. A CSR listing of reason for screen failure will be provided for all subjects who screen failed.

9.0 Study Drug Exposure and Compliance

For the Safety Analysis Set population, study drug exposure will be summarized through the study as follows:

9.1 Study Drug Exposure

The duration (days) of exposure to study drug will be summarized using the number of subjects treated, mean, standard deviation, minimum, median, and maximum. Duration of exposure is defined the number of days since first dose of study drug through the last dose date plus 14 days. For interim analysis at Week 24, the Week 24 dosing date will be used instead of last dose plus 14 days only for ongoing subjects. In addition, the number and percentage of subjects exposed to study drug will be summarized for the following duration intervals.

1 – 15 days
16 – 29 days
30 – 57 days
58 – 85 days
86 – 113 days
114 – 141 days
142 – 169 days
170 – 197 days
198 – 225 days
226 – 253 days
254 – 281 days
282 – 309 days
310 – 337 days
338 – 365 days
> 365 days

Exposure to study drug (total patient years) will be summarized.

Cumulative Dose (mg)

Cumulative dose is derived as dose per administration times the number of injections given during the study. Cumulative dose will be summarized using the number of subjects treated, mean, standard deviation, minimum, median, and maximum.

The Number of Study Drug Injections

The number of injections received at each scheduled time point by subject will be summarized with numbers.

9.2 Compliance

Compliance (%) is defined as the number of adalimumab injections received divided by the number of adalimumab injections planned (rounded to 0.1) during the subject's participation in the study. For subjects who discontinued the study, planned study drug injections counted until the last dose date or the date of last efficacy or vital sign measurement.

9.3 Study Drug Dose

80 mg starting at Baseline (Week 0) and 40 mg eow on and after Week 2 until Week 50. Dose escalation to 80 mg eow is allowed for subjects who do not have appropriate response and meeting dose escalation criteria on or after Week 8. Dose reduction is not allowed after dose escalation until the study end. Treatment of study drug will not occur at Week 52.

The number of adalimumab injections received by subjects will be summarized.

10.0 Efficacy Analysis**10.1 General Considerations**

This study is an open-label study without any comparator. The significant level is not defined, and descriptive statistics will be provided. These include the number of

observations, mean, standard deviation, minimum, median, and maximum for continuous variables; and number and percent for discrete variables. The exact 95% confidence intervals will be provided for the proportions. The analysis will be performed using SAS® (SAS Institute Inc., Cary, NC, USA). All efficacy analyses will be performed on the FAS.

10.2 Efficacy Analysis

This section provides the details of the primary efficacy analysis for the study.

Primary Efficacy Endpoint

The primary efficacy endpoint is the proportion of subjects achieving Clinical Response (CR) at Week 16. CR is defined as reduction of skin score of at least 1 (if the subject's Baseline skin score is 3) or at least 2 (if the subject's Baseline skin score is 4 or higher) relative to Baseline, according to JDA severity index of GPP in GPP Medical care guideline 2014 in Japan.

Table 6. The clinical response categories were defined according to the total skin score at Baseline

Skin score at Baseline	Reduction in skin score						Increase in Skin Score
	Score = 0	$\geq \Delta 3$	$\Delta 2$	$\Delta 1$	$\Delta 0$		
4 – 9	Remission	Improvement	Improvement	Minimal improvement	Unchanged	Worsened	
3	Remission	Remission	Improvement	Improvement	Unchanged	Worsened	

Imputation Method Used for the Primary Efficacy Analysis

Missing data will be imputed using the non-responder imputation (NRI) approach. For details on missing data imputation methods, refer to Section 6.

10.3 Secondary Efficacy Analyses

Discrete variables will be summarized by counts and percentages, and continuous variables will be summarized by descriptive statistics on the items below at each visit.

The subjects who have missing data for any reason such as early terminated subjects will be included into analysis using NRI for discrete variables or LOCF for continuous variables.

- Proportion of subjects achieving Clinical Response (expect Week 16, which is the primary endpoint).
- Proportion of subjects achieving remission.
- Change from the Baseline in total GPP score (skin and systemic/laboratory test).
- Change from the Baseline in JDA severity index of GPP.
- Change and Percent change from the Baseline in total skin score.
- Change from the Baseline in total systemic/laboratory test score.
- Change from the Baseline in score of erythema area (overall) and BSA (BSA of GPP).
- Change from the Baseline in score of erythema area with pustule and BSA.
- Change from the Baseline in score of edema area and BSA.
- Change from the Baseline in Body temperature.
- Change from the Baseline in WBC.
- Change from the Baseline in hs-CRP.
- Change from the Baseline in serum Albumin.
- Proportion of subjects achieving "Mild" in JDA severity index of GPP for patients with "Moderate" or "Severe" at the Baseline.
- Proportion of subjects achieving Treatment Success in PGA (reduction of 2 grades).
- Change from the Baseline in PGA grade.
- Proportion of subjects achieving PGA 0/1 for patients with PGA grade at least 2 at Baseline.
- Proportion of subjects achieving PASI 90.

- Proportion of subjects achieving PASI 75.
- Proportion of subjects achieving PASI 50.
- Change and Percent change from the Baseline in PASI score.
- Proportion of subjects achieving DLQI = 0.
- Change from the Baseline in DLQI score.
- Change from the Baseline in SF-36 score.
- Proportion of subjects taking systemic co-medication for GPP (etretinate, MTX, oral steroids, cyclosporine).
- Proportion of subjects taking topical co-medication for GPP (corticosteroid, vitamin D3, tacrolimus).

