For subjects who are on oral steroids at the Baseline, their steroid dose must be tapered off for 4 weeks (until Week 4) and withdrawn for the rest of the study period. For subjects who are on cyclosporine at the Baseline, the treatment must be tapered off for 8 weeks (until Week 8) and withdrawn for the rest of the study period.

Throughout the study, subjects who are on etretinate (maximum dose of 20 mg/day at the Baseline), MTX, azathioprine, or salazosulfapyridine will be continued on their stable dose or have their dose of GPP-specific concomitant medications decreased as specified in Section [5.2.3.2](#). Dose escalation is not allowed for these treatments.

No study drug will be administered at the final visit.

70-Day Follow-Up/Premature Discontinuation

Subjects may discontinue adalimumab treatment at any time during study participation (Section [5.4](#)). Subjects who end study participation early will have a premature discontinuation (PD) Visit. All subjects will have a follow-up phone call approximately 70 days after the last administration of study drug to obtain information on any new or ongoing AEs.

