5.3.3.2 Secondary Variables

Secondary efficacy variables, to be analyzed at each scheduled visit, include:

1. Proportion of subjects achieving Clinical Response (expect Week 16, which is the primary endpoint).
2. Proportion of subjects achieving remission.
3. Change from the Baseline in total GPP score (skin and systemic/laboratory test).
4. Change from the Baseline in JDA severity index of GPP.
5. Change and Percent change from the Baseline in total skin score.
6. Change from the Baseline in total systemic/laboratory test score.
7. Change from the Baseline in score of erythema area (overall) and BSA (BSA of GPP).
8. Change from the Baseline in score of erythema area with pustule and BSA.
9. Change from the Baseline in score of edema area and BSA.
10. Change from the Baseline in Body temperature.
11. Change from the Baseline in WBC.
12. Change from the Baseline in hs-CRP.
13. Change from the Baseline in serum Albumin.
14. Proportion of subjects achieving "Mild" in JDA severity index of GPP for patients with "Moderate" or "Severe" at the Baseline.
15. Proportion of subjects achieving Treatment Success in PGA (reduction of 2 grades).
16. Change from the Baseline in PGA grade.
17. Proportion of subjects achieving PGA 0/1 for patients with PGA grade at least 2 at Baseline.
18. Proportion of subjects achieving PASI 90.

19. Proportion of subjects achieving PASI 75.
20. Proportion of subjects achieving PASI 50.
21. Change and Percent change from the Baseline in PASI score.
22. Proportion of subjects achieving DLQI = 0.
23. Change from the Baseline in DLQI score.
24. Change from the Baseline in SF-36 score.
25. Proportion of subjects taking systemic co-medication for GPP (etretinate, MTX).
26. Proportion of subjects taking topical co-medication for GPP (corticosteroid, vitamin D3, tacrolimus).

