8.1.4.2 Secondary Efficacy Variables

Discrete variables will be summarized by counts and percentages, and continuous variables will be summarized by descriptive statistics on the items below at each visit.

The subjects who have missing data for any reason such as early terminated subjects will be included into analysis using NRI for discrete variables or LOCF for continuous variables.

For secondary efficacy variables, see Section [5.3.3.2](#).

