6.5 Definition of Missing Data Imputation

The following methods will be used to impute missing values in the efficacy analyses. In general, missing Baseline and safety data will not be imputed. In addition, an observed case analysis will be performed.

Baseline Value is Missing

Subjects will be excluded from analysis of change from baseline if baseline evaluation is missing.

Non-Responder Imputation (NRI)

The NRI approach is used for binary efficacy variables. These variables can take values of 'Achieved' or 'Not Achieved' or may be missing for any reason including discontinuation from study. According to the NRI imputation approach, all missing value will be considered as 'Not Achieved.'

Last Observation Carried Forward (LOCF)

For continuous variables, the following rules will be used for the LOCF approach:

1. Baseline and pre-baseline values will not be used to impute the missing post-baseline values.
2. Missing values after Study Day 1 will be imputed using the latest non-missing values after Day 1 and prior to the missing value. If there are no non-missing values after baseline, then the LOCF value will be missing.

Observed Cases (OC)

Observed case analysis will be performed such that missing values will not be imputed.

Imputation of Missing Dates

For baseline, efficacy, and safety parameters, if the day and/or month are missing, the following conventions will be used to impute the missing dates:

- 01 for missing start day
- End of month for missing end day

- January 1st for missing start month
- December 31st for missing end month

In case of missing or partially missing dosing dates, the dates will not be imputed.

In case of missing or partially missing adverse event start and stop dates, the dates will be imputed by comparing to the first dosing date so that the corresponding adverse events will be made treatment-emergent, whenever possible.

Rounding

Rounding will be performed only for presentation of results. No rounding will be performed before or during computations. The ROUND function of SAS will be used to round results for presentation.

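### Non-responder imputation is applied to two proportions of subjects taking GPP co-medication without saying what counts as achieved, so visits after dropout are miscounted on either coding (minor)

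*SAP*

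**What the plan says.** SAP 10.3 introduces the secondary variables with one missing-data rule: "early terminated subjects will be included into analysis using NRI for discrete variables or LOCF for continuous variables". Protocol 8.1.4.2 has the same rule; subjects with missing data "will be included into analysis using NRI for discrete variables or LOCF for continuous variables". Neither makes an exception for any item.

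The last two items in the SAP list are:
- "Proportion of subjects taking systemic co-medication for GPP (etretinate, MTX, oral steroids, cyclosporine"
- "Proportion of subjects taking topical co-medication for GPP (corticosteroid, vitamin D3, tacrolimus"

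SAP 6.5 defines NRI for binary efficacy variables that are either *Achieved* or *Not Achieved*, or that "may be missing for any reason including discontinuation from study". Under NRI "all missing value will be considered as" *Not Achieved*. The same section adds an observed-case analysis without imputation.

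Protocol 5.2.3.2 has changes in concomitant medication assessed at each visit from Baseline to Week 52 or PD. SAP 6.4 assigns actual visits, including early termination visits, to the scheduled analysis windows.

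The systemic item in Protocol 5.3.3.2 is narrower: "Proportion of subjects taking systemic co-medication for GPP (etretinate, MTX". The SAP adds oral steroids and cyclosporine. Protocol 5.1 and 5.2.3.2 require oral steroids taken at Baseline to be tapered off by Week 4. For cyclosporine, Protocol 5.1 says "the treatment must be tapered off for 8 weeks (until Week 8) and withdrawn for the rest of the study period".

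**The concern.** NRI is conservative when the counted state is favourable, because a subject with no data is then denied the good outcome. The response proportions in SAP 10.3 are of that kind. The two co-medication proportions are not: being counted means still needing background treatment. The words *Achieved* and *Not Achieved* have no obvious meaning for them, and neither document supplies one.

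The programmer therefore has to choose. If *Achieved* is coded as taking, a user who leaves the study is tabulated as not taking at every later visit, and dropout looks like a reduction in background therapy. If *Achieved* is coded as not taking, a non-user who leaves is tabulated as taking. The same data can give different tables, and each coding misstates the status of some subjects who drop out.

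**Working it through.** The plan gives no figure for these two proportions, so there is none to reproduce. The check takes the rule as written and applies it to assumed counts.

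**Inputs.** From the documents: target of 10 subjects (SAP 4.3); missing set to *Not Achieved* (SAP 6.5); exact 95% confidence intervals for proportions (SAP 10.1). Assumed, because the documents do not give them: numbers of users and dropouts. No other subject is missing or changes status, and the visit examined falls after the PD visit.

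**Formulas.** Let *n* be the number in the FAS and *u* the number of users. Let *a* be the users and *b* the non-users who drop out.
- *Achieved* = taking: reported use = (u − a)/n.
- *Achieved* = not taking: reported use = (u + b)/n, because all dropouts are set to taking.
- Observed cases: (u − a)/(n − a − b).
- Gap between the codings: (a + b)/n, which is the share of the FAS that has dropped out.

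**Example: n = 10, u = 6, a = 2, b = 1**

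| Method | Count | Result | Exact 95% CI |
|---|---|---|---|
| NRI, *Achieved* = taking | (6 − 2)/10 = 4/10 | 40.0% | 12.2–73.8% |
| NRI, *Achieved* = not taking | (6 + 1)/10 = 7/10 | 70.0% | 34.8–93.3% |
| Observed cases | 4/(10 − 3) = 4/7 | 57.1% | 18.4–90.1% |
| Last status carried forward | 6/10 | 60.0% | 26.2–87.8% |

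The gap between the codings is (2 + 1)/10 = 30 points. By the same formula it is 0 points with no dropout, 10 with one and 20 with two.

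**Users only dropping out: n = 10, u = 5, b = 0**

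| User dropouts | NRI, *Achieved* = taking | Observed cases |
|---|---|---|
| 0 | 5/10 = 50.0% | 5/10 = 50.0% |
| 1 | 4/10 = 40.0% | 4/9 = 44.4% |
| 2 | 3/10 = 30.0% | 3/8 = 37.5% |
| 3 | 2/10 = 20.0% | 2/7 = 28.6% |

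Observed cases also fall when users leave, but less steeply, and the shrinking denominator shows why. Under NRI the denominator stays at 10 and the loss cannot be seen.

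**Which visits are affected.** NRI replaces only missing values, so recorded status is used at every attended visit. The PD visit counts in the window where it falls, and the late efficacy windows in SAP Table 2 are wide (Week 24 is Days 142–211; Week 52 is Days 310–421). Only scheduled visits after PD are imputed, so a late dropout may have few of them.

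**The case against.** The strongest reply is that this is an unclear label, not a plan to count dropouts favourably. SAP 6.5 confines NRI to variables with an *Achieved* state, and the co-medication items are the ones worded as taking rather than achieving. They could be read as outside NRI altogether. That reading is possible, but SAP 10.3 applies NRI to the discrete variables in its list and names early terminators as covered. The general default to non-missing data in SAP 6.0 holds only where nothing else is specified. What stands is that no favourable intent can be inferred.

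A reader might also infer that the status recorded up to discontinuation is thrown away. The documents do not support this: imputation touches only missing values, and SAP 6.4 places early termination visits in windows.

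A third reply is that an observed-case analysis is already planned. This stands, and the fix uses it. It does not settle the coding of the NRI table, or which of the two tables is to be read first. The summary in SAP 7.3 is by generic name with no visit breakdown stated, so it does not replace a by-visit proportion.

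Finally, a reader might treat last status carried forward as the true answer. Protocol 5.4.1 leaves treatment after discontinuation to the investigator's judgment, so last on-study status is weak evidence of later use. The 60% in the example is another assumption, not a benchmark.

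**Conclusion.** The point holds at minor severity. For scheduled visits after PD, the written rule misclassifies some dropouts whichever way *Achieved* is coded. With a FAS of 10, the two codings differ by 10 points per dropout. The 30-point example needs 3 dropouts among 10 subjects, and neither document gives a dropout rate or a number of users.

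The consequence is limited. Both proportions are secondary, and SAP 10.1 defines no significance level for efficacy and plans descriptive statistics. The primary endpoint counts a favourable state, so NRI works in the proper direction there.

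The wider systemic list in the SAP adds a point of interpretation. Oral steroids and cyclosporine must be withdrawn by Weeks 4 and 8, so later non-use of them is largely mandated. The SAP does not claim such non-use as benefit, but a pooled row invites that reading. The difference from the supplied Protocol's list should not itself be called an error: SAP 3.0 works from a protocol dated 06 April 2017, while the supplied synopsis is dated 08 June 2015.

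**What to change.** In SAP 10.3, exempt the two co-medication proportions from NRI. Make the observed-case proportion already planned in SAP 6.5 their main presentation, with the number of subjects on study at each visit beside it. Last status carried forward is at most an optional sensitivity display, labelled as an assumption.

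Tabulate oral steroids and cyclosporine in a separate row from etretinate and MTX, so that protocol-required withdrawal is not mixed with discretionary change. This also keeps any carried-forward display from showing use beyond Week 4 or Week 8 in the row for etretinate and MTX.

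The cost is a sentence of SAP wording and one more table row, with no new data. The drawback is that the denominator varies by visit and the proportion describes only subjects still on study. That is why the number on study must appear with it.

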5.2.3 Prior and Concomitant Therapy

5.2.3.1 Prior Therapy

Any non-GPP medication or vaccine (including over-the-counter or prescription medicines, vitamins, mineral supplements, and herbal supplements) that the subject is receiving within 30 days prior to Baseline, is receiving at the time of Enrollment, and/or receives during the study, must be recorded along with the reason for use, date(s) of administration including start and end dates, and dosage information including dose, route and frequency on the appropriate electronic case report form (eCRF). Medication for PPD test and injection solvents does not need to record as far as adverse events derived from these drugs are not occurred.

GPP-specific medications and therapies (including but not limited to cyclosporine, etretinate, MTX, oral or topical corticosteroids, topical vitamin D3, phototherapy, or GMA) that the subject has received within 90 days of Baseline should be recorded on the appropriate page of the eCRF and should include the date(s) of administration and dosages, and reason(s) for termination of the treatment (if appropriate). Subjects who failed to respond (within the past 1 year) or were intolerant (within the past 5 years) to treatment will have date(s) of administration, dosages including maximum dose, and reasons for discontinuation recorded in appropriate eCRF, as long as these information is available in the medical records.

For subjects previously treated with infliximab, the infliximab history will be recorded, including the duration of therapy, maximum dose, reason for use and reason(s) for termination of treatment.

The AbbVie SDP identified in Section [6.1.5](#) should be contacted if there are any questions regarding concomitant or prior therapies.

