5.2.3.2 Concomitant Therapy

Doses of etretinate (tapered to 20 mg/day at maximum dose prior to the Baseline), MTX, azathioprine, or salazosulfapyridine taken at Baseline will be continued and remain stable throughout the study. Doses may be decreased or terminated in the event of moderate-to-severe treatment-related toxicities or improvement of GPP skin lesion according to the discretion of the investigator. Dose escalation of these treatments will not be allowed.

Doses of topical corticosteroids ("Very strong," "Strong," "Medium" and "Weak" in Japanese classification), topical vitamin D3, or topical tacrolimus taken at the Baseline will be continued without dose escalation. Dose escalation (increase of amount for use) of topical corticosteroids is allowed only to use lower classes of drugs. Doses may be decreased or terminated in the event of moderate-to-severe treatment-related toxicities or improvement of GPP skin lesion according to the discretion of the investigator.

For subjects who are on oral steroids at the Baseline, their steroid dose must be tapered off for 4 weeks (until Week 4) and withdrawn for the rest of the study period. For subjects

who are on cyclosporine at the Baseline, the treatment must be tapered off for 8 weeks (until Week 8) and withdrawn for the rest of the study period.

Changes in all concomitant medications will be assessed at each study visit from Baseline (Week 0) through Week 52/PD Visits. Any changes will be documented, including the reason for the change of dose will be documented in the source documents and captured on the appropriate eCRF page.

Prophylaxis treatment with isoniazid for TB will be recorded. Even if a subject prematurely discontinues the study, isoniazid treatment should be continued for 9 months considering the best interest of the subject at the discretion of the investigator.

Any vaccine (except for live vaccines) administered during the study will be recorded in the eCRF as a concomitant medication.

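### The systemic co-medication endpoint does not list azathioprine or salazosulfapyridine, so a subject on either drug and no listed drug is counted as not on systemic co-medication

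*SAP*

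**What the plan says.** SAP 10.3 includes, among the secondary variables summarized at each visit, the "Proportion of subjects taking systemic co-medication for GPP (etretinate, MTX, oral steroids, cyclosporine"). The matching item in Protocol 5.3.3.2, no. 25, is the "Proportion of subjects taking systemic co-medication for GPP (etretinate, MTX"). Neither list is worded as examples.

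On permitted background treatment, Protocol 5.1 says that subjects on etretinate, "MTX, azathioprine, or salazosulfapyridine will be continued on their stable dose or have their dose of GPP-specific concomitant medications decreased". Protocol 5.2.3.2 repeats the permission for the same four drugs: "MTX, azathioprine, or salazosulfapyridine taken at Baseline will be continued and remain stable throughout the study". It then adds: "Doses may be decreased or terminated in the event of moderate-to-severe treatment-related toxicities or improvement of GPP skin lesion".

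The two classes found only in the SAP list are handled differently. Protocol 5.1 states: "For subjects who are on oral steroids at the Baseline, their steroid dose must be tapered off for 4 weeks (until Week 4"). Cyclosporine is to be tapered off by Week 8. Both are then withheld for the rest of the study.

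**The concern.** The endpoint is named as systemic co-medication for GPP. The protocol identifies four systemic drugs that may accompany adalimumab for the full 52 weeks, and the endpoint counts two of them. The SAP does widen the protocol's list, but only with the two classes that must be gone by Week 4 and Week 8.

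This looks more like an oversight than a choice. The companion topical endpoint in SAP 10.3 names corticosteroid, vitamin D3 and tacrolimus, which are exactly the three topical classes that Protocol 5.2.3.2 permits. Only the systemic list falls short of what is permitted, and neither document gives a reason.

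At stake is whether a descriptive rate of background treatment, in an open-label single-arm study of 10 subjects, means what its label says.

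**Working it through.** **Step 1. Set the lists side by side.** Permission comes from Protocol 5.1 and 5.2.3.2, and counting from Protocol 5.3.3.2 no. 25 and SAP 10.3.

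| Drug | Permitted | Counted, protocol | Counted, SAP |
|---|---|---|---|
| Etretinate | whole study | yes | yes |
| MTX | whole study | yes | yes |
| Azathioprine | whole study | no | no |
| Salazosulfapyridine | whole study | no | no |
| Oral steroids | until Week 4 | no | yes |
| Cyclosporine | until Week 8 | no | yes |

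Of the four drugs allowed all year, 2 of 4 are counted. After Week 8, a subject who follows the protocol can be counted only through etretinate or MTX, even under the SAP list.

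**Step 2. Who is misclassified.** A subject on azathioprine plus MTX is still counted, through MTX. A subject on azathioprine alone is not. The error therefore affects only subjects who take an omitted drug and no listed drug at that visit.

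**Step 3. Direction and size of the error in level.** Let L be the number on a listed drug at a visit, k the number on an omitted drug only, and n the number analysed.

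- Reported proportion = L/n.
- Proportion with all six drugs or classes counted = (L + k)/n.
- Understatement = k/n, which cannot be negative.

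With n = 10 (Protocol 5.2, assuming that all enrolled subjects enter the FAS), one subject is 1/10 = 10 percentage points. The documents give neither L nor k. For illustration I assume L = 3 and let k run from 0 to 3, with the exact (Clopper-Pearson) 95% intervals that SAP 10.1 prescribes for proportions:

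| k | Reported | All six counted | Exact 95% CI, all six |
|---|---|---|---|
| 0 | 30% | 30% | 6.7% to 65.2% |
| 1 | 30% | 40% | 12.2% to 73.8% |
| 2 | 30% | 50% | 18.7% to 81.3% |
| 3 | 30% | 60% | 26.2% to 87.8% |

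**Step 4. Change over time.** Three constructed cases, each with n = 10:

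- *No distortion.* Two subjects take only an oral steroid and taper off, and one stays on azathioprine alone. The SAP list goes from 2/10 to 0/10, and the full list from 3/10 to 1/10. Both fall by 20 points.
- *Fall overstated.* One subject takes MTX plus azathioprine, stops MTX and stays on azathioprine. The SAP list goes from 1/10 to 0/10, while the full list stays at 1/10. The SAP shows a 10-point fall that did not occur.
- *Fall understated.* One subject on azathioprine alone stops it after improvement, as Protocol 5.2.3.2 allows. The SAP list stays at 0/10, while the full list goes from 1/10 to 0/10. The SAP misses a 10-point fall.

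The sign of the error in the trend therefore depends on the drug combinations, which the documents do not give.

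No figure stated in the protocol or SAP depends on this list, so there is none to reproduce.

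**The case against.** The strongest defence is that the two drugs are not clearly GPP therapy. Protocol 3.0 names etretinate, cyclosporine and infliximab as the approved systemic treatments. Its account of the guideline lists etretinate, cyclosporine, methotrexate and TNF inhibitors. The recording rule in Protocol 5.2.3.1 describes GPP-specific treatment as "including but not limited to cyclosporine, etretinate, MTX, oral or topical corticosteroids, topical vitamin D3, phototherapy, or GMA", and neither drug appears there. Only one sentence, in Protocol 5.1, attaches the GPP-specific label to them; 5.2.3.2 does not use it. On this view the SAP list is a defensible selection that lacks only a stated reason.

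Part of this stands: the label rests on 5.1 alone. But the list in 5.2.3.1 is expressly open, and 5.2.3.2 ties reduction of all four drugs to improvement of GPP skin lesions, which treats them as therapy for the disease. If the exclusion was deliberate, the SAP should say so.

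A second defence is that SAP 7.3 tabulates all concomitant therapy by generic name, so users would be visible. That is true, but 7.3 specifies no proportion by visit and does not feed this endpoint.

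A third is low stakes. Item 25 is one of 26 descriptive secondary variables; SAP 10.1 sets no significance level, and SAP 10.4 makes no multiplicity adjustment. This stands in full and limits the weight of the point.

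The protocol synopsis is dated 08 June 2015, while SAP 3.0 refers to a protocol dated 06 April 2017 that incorporates administrative changes. The difference between the two-drug and four-drug lists may have arisen in between, so nothing here rests on it. Both lists omit the same two drugs.

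**Conclusion.** The point holds as a minor defect of definition. A subject on azathioprine or salazosulfapyridine and no listed drug is counted as not on systemic co-medication at that visit. At n = 10 this understates the proportion by 10 percentage points per such subject, and by nothing if there are none. The text comparison is firm. The size is conditional, because the documents do not give the number of users.

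Four stronger readings are tempting and are not supported:

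- *Every user of the two drugs is counted as untreated.* A user who also takes a listed drug is still counted.
- *The decline over time is exaggerated.* The cases above show no distortion, overstatement and understatement, depending on the combination.
- *The omission creates the early fall as steroids and cyclosporine are withdrawn.* That fall comes from the mandatory taper and would appear equally in a single combined numerator with all six drugs or classes.
- *The endpoint shows how much response occurs alongside systemic treatment.* It is a marginal proportion at each visit, not cross-classified with response, and the subgroups in SAP 10.5 do not use co-medication.

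**What to change.** In SAP 10.3, add azathioprine and salazosulfapyridine to the numerator list. Report one row for the four drugs that may continue (etretinate, MTX, azathioprine, salazosulfapyridine) and a separate row for the two classes with a mandatory taper (oral steroids, cyclosporine), so that the taper is not read as an effect of study treatment. If the two drugs were left out on purpose, state the reason instead. Record the departure from Protocol 5.3.3.2 no. 25 in SAP 12.1.

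No new data are needed, because Protocol 5.2.3.2 already has changes in all concomitant medication assessed at each visit. The cost is a few words in the SAP, a slightly longer program, and a co-medication rate that may look less favourable. Changing the protocol item as well would be an amendment needing ethics committee approval under Protocol 9.1; the SAP change alone is enough to correct the analysis. The change does not touch the primary endpoint, the sample size or the treatment of any subject.
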